6. SUPPORTING DOCUMENTATION

6.1. Appendix 1 Study Population Analyses

A summary of the number of participants in each of the participant level analysis set will be provided.

6.1.1. Participant Disposition

Participant disposition will be summarized by study arms using descriptive statistics:

- Number of maternal participants screened, enrolled, conceived, completed the study as well as those who prematurely withdrew including withdrawal reasons in each arm and overall will be tabulated.
- Number of infant participants enrolled and withdrawn including withdrawal reasons will be tabulated by arm and overall.

6.1.2. Demographic and Baseline Characteristics

These analyses will be performed on the Enrolled set and on the Full Analysis Set.

For all maternal participants, demographic characteristics (e.g., age at previous study vaccine administration <18, 18-24, 25-34 and ≥ 35 years; overall), age at 1st and 2nd pregnancy, gestational age at birth (≥ 37 weeks or < 37 weeks), other baseline and lifestyle characteristics will be summarized by arm using descriptive statistics. The interval in days between previous RSV MAT study delivery and current study pregnancy will be calculated and summarized by arm using descriptive statistics.

For infants, demographic characteristics (e.g., gestational age at time of delivery (≥ 37 weeks; < 37 weeks), sex, weight, length, head circumference, race and ethnicity), and lifestyle characteristics (e.g., living environment, household composition, breastfeeding, passive smoking and extent of contact with children less than 6 YOA) will be summarized by arm using descriptive statistics.

Past medical conditions and current medical conditions as of screening will be summarized respectively.

Demographics and baseline characteristics as well as the lifestyle characteristics may be reported by CCI [REDACTED]

6.1.3. Protocol Deviations

Important protocol deviations will be summarized by arm.

Protocol deviations will be tracked by the study team throughout the conduct of the study. These protocol deviations will be reviewed to identify those considered as important as follows:

- Data will be reviewed prior to freezing the database to ensure all important deviations (without knowing the previous study intervention details if possible) are captured and categorised in the protocol deviations dataset.
- This dataset will be the basis for the summaries of important protocol deviations.
- The summary will include number and percentage of participants with important protocol deviations by deviation category for each study group.
- An individual listing of protocol deviation will also be provided.

Protocol deviations which result in exclusion from the analysis set will also be summarized by arm.

- Data will be reviewed prior to freezing the database to ensure all deviations leading to analysis population exclusions are captured and categorised in the protocol deviations ADaM dataset (note these exclusions are not captured in the SDTM dataset).

In addition to the overall summary of important protocol deviations, separate summaries may be produced for important protocol deviations related to COVID-19, and important protocol deviations not related to COVID-19 respectively if deemed necessary.

Summary of important protocol deviations leading to elimination will be tabulated by arm. An individual listing will also be provided.

6.1.4. Prior and Concomitant Medications

Concomitant medications and vaccinations will be coded using the GSK Drug dictionary and be summarized respectively.

- The number and percentage of maternal participants taking concomitant medications /vaccinations from pregnancy until Day 42 post-delivery will be summarized by arm. A listing will also be provided.
- The number and percentage of infants taking concomitant medications/ vaccinations from birth up to 42 days after birth will be summarized by arm. A listing will also be provided.

6.1.5. Study Intervention Compliance

Not applicable.

6.1.6. Additional Analyses Due to the COVID-19 Pandemic

Depending on how the Covid-19 situation evolves, the SAP might be amended to reflect the analysis corresponding to Covid-19.

6.2. Appendix 2 Data Derivations Rule

6.2.1. Study Period

The study period starts from the date of start of any pregnancy conceived after RSV MAT vaccination (RSVPreF3) or control vaccination in RSV MAT studies or from the date of current study enrollment, whichever date is earlier. The study period ends at current study enrollment for retrospective cohort participants. The study period ends at 2 years+2 months post vaccine/control for prospective cohort participants who are not pregnant at 2 years post vaccine/control. The study period ends at Day 42 post-delivery for prospective cohort participants who are pregnant at 2 years post vaccine/control or at study enrollment.

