1.2. Schema

Figure 1 Overall Study design overview

[figure not shown]

AESI: Adverse Events of Special Interest; **SAE:** Serious Adverse Event; **MAEs:** Medically attended Adverse Events

*2 years+2 months post vaccine/control to give time for the participant to be aware of a pregnancy if it is conceived very close to 2 years post-vaccination. The retrospective cohort will also include participants who have not reached 2 years+2 months post vaccine/control prior to/at enrollment but are a Woman of Nonchildbearing Potential (WONCBP) as defined in Section 10.3.1.2 at study enrollment, or recipient of bilateral tubal ligation prior to study enrollment.

**For participants enrolled in prior studies of pregnant women (i.e., MAT-004, MAT-009, MAT-012), this study will include pregnancies conceived after the prior study pregnancy in which RSVPreF3 vaccination (or control) was administered.

*** For participants enrolled in prior RSV MAT studies i.e., RSV MAT-001, RSV MAT-004, RSV MAT-009, RSV MAT-010, RSV MAT-011, RSV MAT-012 and RSV MAT-039.

Figure 2 Study design overview- Prospective cohort

*Contacts every 6 months up to 2 years (+2 months) post-vaccine/control (received as part of prior RSV MAT study participation), unless a pregnancy conceived post-vaccine/control is reported.

** Once a pregnancy is reported, the participant is followed monthly during pregnancy until delivery, then again at Day 42 post-delivery. Pregnancy follow-up will include all pregnancies ongoing at enrollment or newly conceived during follow-up within 2 years post vaccine/control. If Day 42 post-delivery is <2 years+2 months, the woman returns to contacts every 6 months until 2 years (+2 months) post-vaccine/control.

***In addition to the planned study contacts, additional unplanned visits or medical procedures can be done as per the investigator's discretion.

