4. STUDY DESIGN

4.1. Overall design

See Section 1.2 for the study schematic diagram.

This study will be a combination of retrospective and prospective cohort design with two groups. RSVPreF3 vaccine group will include participants who received RSVPreF3 vaccine in RSV MAT studies and control group will include participants who received any control (placebo, Tdap or influenza vaccine) during *prior* RSV MAT studies.

- **Retrospective cohort**

- Current study participants who are more than 2 years after vaccination/control and are not currently pregnant at the time of study enrollment will be included in this study cohort.
 - Participants previously enrolled in *prior* RSV MAT studies will be included in this cohort.
 - For participants enrolled in prior studies of pregnant women (i.e., MAT-004, MAT-009, MAT-012), data collection for this cohort will not include the prior study pregnancy.
- Medical data related to any pregnancy conceived post RSVPreF3 vaccine or any control (placebo, Tdap or influenza vaccine) through study enrollment (even if the pregnancy was conceived after 2 years post-vaccine/control) will be collected retrospectively from the date of start of current study pregnancy up to Day 42 (approximately 6 weeks) post-delivery.
- Infants will be enrolled with the maternal participants at Visit 1 and all relevant medical data until Day 42 post-delivery will be retrieved.

- **Prospective cohort:**

- Current study participants who are within 2 years+2 months after vaccination/control or with ongoing pregnancies (pregnancies prior to Day 42 post-delivery) at the time of study enrollment will be included in this study cohort.
- Study participants enrolled in *prior* RSV MAT studies will be included in this study cohort.
 - For participants enrolled in prior studies of pregnant women (i.e., MAT-004, MAT-009, MAT-012), data collection for this cohort will not include the prior study pregnancy.
- All participants will be followed up for 2 years+2 months post RSVPreF3 or control vaccination to record any pregnancy conceived within 2 years post vaccine/control. If the participant is pregnant at 2 years post-vaccine/control, study follow-up will continue until day 42 post-delivery.

Note: Pregnancies reported during prospective follow-up at approximately 2 years+2 months that were conceived after 2 years post-vaccine/control will not be included in the study.

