- Medical data related to any pregnancy conceived post RSV MAT (RSVPreF3) vaccine and any control (placebo, Tdap or influenza vaccine) will be collected from the date of start of current study pregnancy up to day 42 (approximately 6 weeks) post-delivery.
- Infants will be enrolled at Delivery and all relevant medical data until Day 42 post-delivery will be collected.
- **Type of study and design:** A safety follow-up cohort study.
- **Study period:** *The* study period starts from the date of start of any pregnancy conceived after RSV MAT vaccination (RSVPreF3) or control vaccination in RSV MAT studies or from the date of current study enrollment, whichever date is earlier. The study period ends at current study enrollment for retrospective cohort participants. The study period ends at 2 years+2 months post vaccine/control for prospective cohort participants who are not pregnant at 2 years post vaccine/control. The study period ends at Day 42 post-delivery for prospective cohort participants who are pregnant at 2 years post vaccine/control **or at study enrollment.**
- **Number of participants:** All adolescent or adult study participants (approximately 8240) from the above-mentioned RSV MAT studies will be considered for enrollment based on the eligibility criteria. Approximately 650 enrolled study participants are estimated to have at least one pregnancy of interest for this study (see Section 9.5 for detailed calculations). Even approximately 300 participants with pregnancy information included in the study would still provide reasonable precision to detect and estimate most of the events of interest in the study.

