4.4. End-of-study definition

A participant is considered to have completed the study if the participant has completed all periods of the study including the last contact (study conclusion). This last contact can be either 1) at current study enrollment for retrospective cohort participants, 2) at 2 years+2 months post vaccine/control for prospective cohort participants who are not pregnant at 2 years post vaccine/control, or 3) at Day 42 post-delivery for prospective

cohort participants who are pregnant at 2 years post vaccine/control ***or who are pregnant at enrollment***. The study may be terminated earlier if other research demonstrates no impact of vaccination on pregnancies conceived post-vaccination.

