1.2. Study Design

Overview of Study Design and Key Features

Figure 2 Study design overview- Prospective cohort

*Contacts every 6 months up to 2 years (+2 months) post-vaccine/control (received as part of prior RSV MAT study participation), unless a pregnancy conceived post-vaccine/control is reported.

** Once a pregnancy is reported, the participant is followed monthly during pregnancy until delivery, then again at Day 42 post-delivery. Pregnancy follow-up will include all pregnancies ongoing at enrolment or newly conceived during follow-up within 2 years post vaccine/control. If Day 42 post-delivery is <2 years+2 months, the woman returns to contacts every 6 months until 2 years (+2 months) post-vaccine/control.

***In addition to the planned study contacts, additional unplanned visits or medical procedures can be done as per the investigator's discretion.

Design Features

Study Type: A safety follow-up cohort study of interventional clinical trials.

Experimental design: Phase IIIB, non-randomized, open label, multi-country, cohort study to describe the safety of study participants who received RSVPreF3 maternal vaccination (any dose) or controls from previous RSV MAT studies

Study Population: All study participants from RSV MAT studies who have received either RSVPreF3 vaccine or control (placebo, Tdap only, influenza vaccine only) will be eligible to be included in this study.

Duration of the study: The study period starts from the date of start of any pregnancy conceived after RSV MAT vaccination (RSVPreF3) or control vaccination in RSV MAT studies or from the date of current study enrollment, whichever date is earlier. The study period ends at current study enrollment for retrospective cohort participants. The study period ends at 2 years+2 months post vaccine/control for prospective cohort participants who are not pregnant at 2 years post vaccine/control. The study period ends at Day 42 post-delivery for prospective cohort participants who are pregnant at 2 years post vaccine/control or who are pregnant at enrollment.

Study intervention

Not applicable.

Study intervention

Not applicable.

Assignment

| Overview of Study Design and Key Features | |
|---|---|
| Concomitant Therapy | Not applicable. |
| Interim Analysis | Not applicable. |
| End-of-study definition | The participant has completed all periods of the study including the last contact (study conclusion). |

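### Women pregnant at enrolment but still within 2 years of vaccine/control have two incompatible end-of-follow-up rules, and one of them can miss repeat pregnancies

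*SAP*

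**What the plan says.** **Day-42 rule.** SAP 6.2.1: "The study period ends at Day 42 post-delivery for prospective cohort participants who are pregnant at 2 years post vaccine/control or at study enrollment". SAP 1.2 has the same rule. Protocol 4.1 (Study period) reads "The study period ends at Day 42 post-delivery for prospective cohort participants who are pregnant at 2 years post vaccine/control" and goes on to add women pregnant at enrolment. Protocol 4.4 and Table 2 footnote c do likewise. None of these places limits the rule by time since vaccine/control.

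**2 years+2 months rule.** The Figure 2 footnote, printed in both documents, expressly covers women pregnant at enrolment: "Pregnancy follow-up will include all pregnancies ongoing at enrolment or newly conceived during follow-up within 2 years post vaccine/control" (SAP 1.2). It then directs: "If Day 42 post-delivery is <2 years+2 months, the woman returns to contacts every 6 months until 2 years (+2 months) post-vaccine/control" (Protocol 1.2). Protocol 4.1, prospective cohort: "All participants will be followed up for 2 years+2 months post RSVPreF3 or control vaccination to record any pregnancy conceived within 2 years". The sentence of SAP 6.2.1 just before the Day-42 rule reads: "The study period ends at 2 years+2 months post vaccine/control for prospective cohort participants who are not pregnant at 2 years post vaccine/control". The Table 4 footnote in the protocol names only women pregnant at 2 years as concluding at Day 42.

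**A narrower statement.** Protocol 5.1.2 applies the Day-42 end to women who had already passed 2 years when they enrolled. The study-period and end-of-study definitions do not carry that limit.

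**The concern.** A woman who enrols pregnant before 2 years, and is no longer pregnant at 2 years, meets both rules and gets two different end dates. SAP 6.2.1 alone gives her both, in consecutive sentences, and nothing says which prevails.

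The secondary endpoint covers any pregnancy conceived within 2 years. If a site follows the Day-42 rule, it stops looking for pregnancies while part of her window is still open. The part lost depends on how the enrolment pregnancy ended, because a shorter pregnancy brings Day 42 forward. Ascertainment of repeat pregnancies would then vary with the outcome of the previous pregnancy and with the section a site happened to follow.

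**Working it through.** **The plan's own figure.** Protocol Table 4 gives 2 years+2 months as 790 days. 2 × 365 + 2 × 30 = 790, so it reproduces. The conception window is 2 × 365 = 730 days.

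**Inputs from the documents**
- Vaccination stopped on 28 February 2022 (Protocol 2.2). That date is used because it leaves the most window open.
- Amendment 2, which according to the protocol's change table added the pregnant-at-enrolment wording, is dated 21 June 2023 (Protocol 10.7). That is day 478 after 28 February 2022.
- The study start is assumed to be 7 December 2022 (Protocol 9.5, SAP 5). That is day 282.

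**Assumptions, not in the documents**
- The woman is 8 weeks pregnant at enrolment. The pregnancy ends either in a loss at 10 weeks (14 days later) or a delivery at 40 weeks (32 × 7 = 224 days later).
- Day 42 is counted from the end of the pregnancy. The documents anchor it to delivery and give no anchor for a loss or termination.

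**Formulas.** Day-42 end = enrolment day + days to end of pregnancy + 42. Window lost = 730 − end, floored at 0. Follow-up lost = 790 − end.

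| Enrolment | Outcome | Day-42 end | Window lost | Follow-up lost |
|---|---|---|---|---|
| 21 Jun 2023, day 478 | Loss, 10 weeks | 478 + 14 + 42 = 534 | 196 days (27%) | 256 days |
| 21 Jun 2023, day 478 | Delivery, 40 weeks | 478 + 224 + 42 = 744 | 0 | 46 days |
| 7 Dec 2022, day 282 | Loss, 10 weeks | 282 + 14 + 42 = 338 | 392 days (54%) | 452 days |
| 7 Dec 2022, day 282 | Delivery, 40 weeks | 282 + 224 + 42 = 548 | 182 days (25%) | 242 days |

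Under the 2 years+2 months rule, window lost is 0 in every row.

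The two end dates for one enrolment day differ by 224 − 14 = 210 days, which is the dependence on outcome. Whatever the gestational ages, a woman enrolled at day 478 cannot lose more than 730 − 478 = 252 days (35%). The loss shrinks with later enrolment or earlier vaccination.

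**Who is affected.** Only women enrolled before 2 years whose Day 42 falls before 2 years+2 months. Women who enrol already past 2 years have no conception window left to lose. Women still carrying the enrolment pregnancy at 2 years end at Day 42 after that date, again with no window lost. The number affected cannot be calculated, because neither the share pregnant at enrolment nor the repeat-conception rate is given.

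**The case against.** **The intent can be inferred.** Protocol 5.1.2 ties the Day-42 end to women past 2 years, and Figure 2 tells sites what to do for the rest. This is the best defence, and it probably describes what was meant. It does not settle the matter. Five places state the rule without the limit, and the change table's rationale for the added wording also states it without the limit. That sites actually discharged women early is not shown.

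**The primary endpoint is safe.** This stands. A woman pregnant at enrolment already has her first study pregnancy, either that one or an earlier one. The possible loss is confined to repeat pregnancies.

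**There is no bias between arms.** The rule is the same in both arms and the study is descriptive. Differential ascertainment would need different early-loss rates by arm, and the documents give no evidence of that.

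**Two stronger readings are tempting.** First, a reader might infer that a later pregnancy would be dropped from the analysis even if it were reported, because SAP 6.2.1 closes the study period at Day 42. The documents do not support this for the main secondary analysis. SAP 4.3.1.1 defines any study pregnancy by conception date alone, and for preterm birth it adds an analysis of all reported pregnancies. The maternal Full Analysis Set refers to Protocol 5.1, not to the study period. Only the risk-factor tabulation in SAP 4.3.2.2 is restricted to the study period, so exclusion is possible there but not stated.

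Second, a reader might take the 392 days (54%) as typical. It pairs the last vaccination date with the assumed start, and that woman's Day 42 (about 1 February 2023) precedes Amendment 2. It is an upper-range figure. The 182 days in the last row does fall under the current wording, since that Day 42 comes on about 30 August 2023.

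**Conclusion.** The contradiction is real, lies in current text of both documents, and occurs within SAP 6.2.1 itself. It needs correcting because the Day-42 rule, applied as written, works against the secondary any-pregnancy endpoint.

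For the latest-vaccinated woman enrolled on the Amendment 2 date, the illustrated loss is 196 days (27%) of the window after an early loss and none after a term delivery. These figures rest on the assumed gestational ages and on counting Day 42 from the end of pregnancy. The end date after a loss is itself undefined in the plan. The effect is on completeness of repeat-pregnancy data in a subgroup of unknown size. No effect on the primary endpoint, and no bias between arms, is established.

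**What to change.** Put one rule in Protocol 4.1, 4.4 and Table 2 footnote c, and in SAP 1.2 and 6.2.1, consistent with Figure 2 and Protocol 5.1.2:
- Prospective women enrolled before 2 years conclude at the later of 2 years+2 months after vaccine/control and Day 42 after the end of a pregnancy ongoing at enrolment or at 2 years.
- Women already past 2 years at enrolment conclude at Day 42.
- State the date from which Day 42 is counted when a pregnancy ends in a loss or termination.
- In SAP 4.3.2.2, say whether a pregnancy conceived within 2 years but reported after a Day-42 conclusion is included.

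**If follow-up is complete.** The latest-vaccinated women reached day 790 on about 28 April 2024, before SAP Amendment 3 of 17 February 2025, so missed contacts may be beyond recovery. The SAP can still fix the rule before analysis. The report should give, by arm and by outcome of the enrolment pregnancy, the number of women who concluded at Day 42 before 2 years+2 months.

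**Cost.** A wording change, one summary table and, where follow-up is still open, a few remote contacts that Figure 2 already schedules. At 180-day spacing, the 256 and 452 days of follow-up lost in the early-loss rows correspond to about two and three contacts, including the final one.

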6.2.2. Study Day and Reference Dates

The safety reference date is the conceived date of the study pregnancy and will be used to calculate study day for safety measures.

The study day is calculated as below:

- Assessment Date = Missing → Study Day = Missing
- Assessment Date < Reference Date → Study Day = Assessment Date – Ref Date
- Assessment Date ≥ Reference Date → Study Day = Assessment Date – Ref Date + 1

6.2.3. Handling of Partial Dates

When partially completed dates (i.e. dates missing a day and/or month) are used in calculations, the following standard rules will be applied:

- A missing day will be replaced by 15
- A missing day and month will be replaced by June 30th.

The following exceptions apply.

| Element | Reporting Detail | | | | | | | | | | |
|---|---|-------------------|--|-----------------------------|--|-----------------|---|---------------------------|---------------|-----------------------------------|---------------|
| General | 
 Partial dates will be displayed as captured in participant listing displays. However, where necessary, display macros may impute dates as temporary variables for sorting data in listings only. In addition, partial dates may be imputed for 'slotting' data to study phases or for specific analysis purposes as outlined below. Imputed partial dates will not be used to derive study day, time to onset or duration (e.g., time to onset or duration of adverse events), or elapsed time variables (e.g., time since diagnosis). In addition, imputed dates are not used for deriving the last contact date in overall survival analysis dataset. | | | | | | | | | | |
| Adverse Events | 
 Partial dates for AE recorded in the CRF will be imputed using the following conventions: 
 
 Missing start day	 
If study intervention start date is missing (i.e. the conceived date of the study pregnancy), then set start date = 1st of month.
 
Else if study intervention start date is not missing:
 
 If month and year of start date = month and year of study intervention start date, then 
 If stop date contains a full date and stop date is earlier than study intervention start date, then set start date= 1st of month. Else set start date = study intervention start date. 
Else set start date = 1st of month.
 	
 
 Missing start day and month	 
If study intervention start date is missing (i.e. participant did not start study intervention), then set start date = January 1.
 
Else if study intervention start date is not missing:
 
 If year of start date = year of study intervention start date, then 
 If stop date contains a full date and stop date is earlier than study intervention start date, then set start date = January 1. Else set start date = study intervention start date. 
Else set start date = January 1.
 	
 
 Missing end day	A '28/29/30/31' will be used for the day (dependent on the month and year).	
 
 Missing end day and month	No Imputation	
 
 Completely missing start/end date	No imputation	
 
 | Missing start day | 
If study intervention start date is missing (i.e. the conceived date of the study pregnancy), then set start date = 1st of month.
 
Else if study intervention start date is not missing:
 
 If month and year of start date = month and year of study intervention start date, then 
 If stop date contains a full date and stop date is earlier than study intervention start date, then set start date= 1st of month. Else set start date = study intervention start date. 
Else set start date = 1st of month.
 | Missing start day and month | 
If study intervention start date is missing (i.e. participant did not start study intervention), then set start date = January 1.
 
Else if study intervention start date is not missing:
 
 If year of start date = year of study intervention start date, then 
 If stop date contains a full date and stop date is earlier than study intervention start date, then set start date = January 1. Else set start date = study intervention start date. 
Else set start date = January 1.
 | Missing end day | A '28/29/30/31' will be used for the day (dependent on the month and year). | Missing end day and month | No Imputation | Completely missing start/end date | No imputation |
| Missing start day | 
If study intervention start date is missing (i.e. the conceived date of the study pregnancy), then set start date = 1st of month.
 
Else if study intervention start date is not missing:
 
 If month and year of start date = month and year of study intervention start date, then 
 If stop date contains a full date and stop date is earlier than study intervention start date, then set start date= 1st of month. Else set start date = study intervention start date. 
Else set start date = 1st of month.
 | | | | | | | | | | |
| Missing start day and month | 
If study intervention start date is missing (i.e. participant did not start study intervention), then set start date = January 1.
 
Else if study intervention start date is not missing:
 
 If year of start date = year of study intervention start date, then 
 If stop date contains a full date and stop date is earlier than study intervention start date, then set start date = January 1. Else set start date = study intervention start date. 
Else set start date = January 1.
 | | | | | | | | | | |
| Missing end day | A '28/29/30/31' will be used for the day (dependent on the month and year). | | | | | | | | | | |
| Missing end day and month | No Imputation | | | | | | | | | | |
| Completely missing start/end date | No imputation | | | | | | | | | | |
| Concomitant Medications/Medical History | 
 Partial dates for any concomitant medications recorded in the CRF will be imputed using the following convention: 
 
 Missing start day	 
If study intervention start date is missing (i.e. participant did not start study intervention), then set start date = 1st of month.
 
Else if study intervention start date is not missing:
 
 If month and year of start date = month and year of study intervention start date, then 
 If stop date contains a full date and stop date is earlier than study intervention start date, then set start date= 1st of month. Else set start date = study intervention start date. 
Else set start date = 1st of month.
 	
 
 Missing start day and month	 
If study intervention start date is missing (i.e. participant did not start study intervention), then set start date = January 1.
 
Else if study intervention start date is not missing:
 
 If year of start date = year of study intervention start date, then 	
 
 | Missing start day | 
If study intervention start date is missing (i.e. participant did not start study intervention), then set start date = 1st of month.
 
Else if study intervention start date is not missing:
 
 If month and year of start date = month and year of study intervention start date, then 
 If stop date contains a full date and stop date is earlier than study intervention start date, then set start date= 1st of month. Else set start date = study intervention start date. 
Else set start date = 1st of month.
 | Missing start day and month | 
If study intervention start date is missing (i.e. participant did not start study intervention), then set start date = January 1.
 
Else if study intervention start date is not missing:
 
 If year of start date = year of study intervention start date, then | | | | | | |
| Missing start day | 
If study intervention start date is missing (i.e. participant did not start study intervention), then set start date = 1st of month.
 
Else if study intervention start date is not missing:
 
 If month and year of start date = month and year of study intervention start date, then 
 If stop date contains a full date and stop date is earlier than study intervention start date, then set start date= 1st of month. Else set start date = study intervention start date. 
Else set start date = 1st of month.
 | | | | | | | | | | |
| Missing start day and month | 
If study intervention start date is missing (i.e. participant did not start study intervention), then set start date = January 1.
 
Else if study intervention start date is not missing:
 
 If year of start date = year of study intervention start date, then | | | | | | | | | | |

| Element | Reporting Detail | |
|---------|-----------------------------------|--|
| | | 
 – If stop date contains a full date and stop date is earlier than study intervention start date, then set start date = January 1. – Else set start date = study. intervention start date. |
| | Missing end day | A '28/29/30/31' will be used for the day (dependent on the month and year). |
| | Missing end day and month | A '31' will be used for the day and 'Dec' will be used for the month. |
| | Completely missing start/end date | No imputation |

